6.3 Interim and Safety Analyses

Adverse events associated with study procedures such as blood draws and pulmonary function testing are expected to be uncommon and limited to mild and transient discomforts. Such events will be monitored through interim reports. Interim reports will also be used to monitor parameters that characterize the conduct of the study, such as pace of recruitment, completeness of scheduled activities, time lags associated with data entry and laboratory testing, as well as QC reports for issues such as inter-observer variability and inter- and intra-laboratory variability. Study statisticians will develop these and other reports. No early stopping rules are in place for this study since there is no treatment and no anticipated risk to participants. Analyses of short-term health outcomes will be conducted after completion of baseline visits. Other interim analyses may be conducted in a blinded fashion so as not to influence investigators or study staff with respect to the conduct or completion of the study.

6.4 Laboratory QA/QC Analyses

Laboratory QA/QC data will be reviewed for evidence of excessive variability and for trends indicating shifts in process control. Data from blind QC samples submitted to laboratories will be analyzed and within-pair coefficients of variation (CV) for internal (within laboratory) consistency samples will be calculated. Inter-laboratory reliability will be investigated by analysis of results of laboratory same-sample analyses. The duplicate blood and urine samples collected from randomly selected individuals in the study (mentioned in Section 2.9.5) will provide specimens for these QA/QC efforts. These individual and pooled samples will be used for quality control purposes such as assessing long-term storage effects and assay batch variability.

6.5 Sample Size Considerations and Power

6.5.1 Estimated sizes of worker (exposed) and non-worker (unexposed) groups

Based on currently available information, we anticipate that when we merge the PEC list, the NIOSH list, the lists of workers from Federal agencies that may be included in this study (e.g., Coast Guard, Fish and Wildlife Service, US Geologic Survey), and other worker lists, and then remove duplicates, persons who provided no contact information, and persons who indicated that they intended to work on clean-up for less than one week (< 0.2% of the early NIOSH roster, but possibly a larger number; likely to be persons with no intention of engaging in clean-up work), the merged list will contain approximately 90,000 names. Based on early NIOSH information, approximately 92% of these persons will be from one of the four most affected Gulf States. Restriction of the workers, for logistical reasons, to persons from the four Gulf States and to those workers from outside of those states who experienced certain high exposures such as to benzene, burning oil, and dispersants will produce a list of approximately 86,000 persons. It is expected that after loss to follow-up, non-response, and refusal, about

55,000 eligible persons (a 60-65% participation rate) will complete the enrollment questionnaire. These 55,000 persons will comprise the full cohort. Among this group, we estimate that about 43,000 (80%) will have engaged in clean-up activities while the remaining 12,000 (~20%) did not. These 12,000 unexposed persons will include up to several thousand Federal responders who engaged only in response activities such as administrative, oversight, or logistical support that did not involve any contact with spill-related oil, oil byproducts, or dispersants.

There are sufficient eligible persons to recruit 15,000 workers and 5,000 controls into the Active Follow-up Sub-cohort, assuming a 40% **participation rate** (after applying sampling probabilities and assuming an 80% response rate for those who have gotten this far) among persons who have already enrolled in the full cohort by participating in the telephone interview. The size of the Active Follow-up Sub-cohort has been capped at 20,000 in light of available funding and statistical power considerations; the base population is large enough that this target is achievable even with a modestly lower participation rate. Based on current information, we estimate that about 26% of the eligible controls are from outside the immediately affected communities. By oversampling these non-local controls, we expect to recruit approximately 1,500 non-local controls and 3,500 local controls, with both groups including Federal controls as described above.

The expected participation rates provided above are reasonable, given anecdotal reports from collaborating federal agencies, media reports, and feedback from community groups and focus groups of clean-up workers that indicate widespread concern about potential health effects from the oil spill among clean-up workers and members of the affected communities. Furthermore, it is possible that the eventual cumulative total of workers will be greater than is currently estimated. We will know the real total only after we have obtained worker lists from other agencies and local communities engaged in clean-up and crossed the lists to identify unique additional workers who did not complete PEC training. *In any case, power calculations indicate that even if actual participation rates turn out to be as much as 20% lower than those indicated above, this study will still be sufficiently powered to achieve its specified aims, with an increase in minimum detectable ORs or differences of less than 10-15%.*

The rest of the full cohort (N~35,000) will comprise individuals to be passively followed who either were not randomly sampled to be part of the Active Follow-up Sub-cohort or who refused to be part of the Active Follow-up Sub-cohort (but participated in the enrollment telephone interview). This represents about 28,000 workers and about 7,000 controls.

Thus, the total size of the full cohort is anticipated to be approximately 55,000 persons (43,000 workers and 12,000 controls), consisting of 20,000 members of the Active Follow-up Sub-cohort (15,000 workers and 5,000 controls [3,500 local and 1,500 non-local, including Federal]) and 35,000 passively followed members of the full cohort (28,000 workers and 7,000 controls).

Based on other prospective observational studies, we anticipate 90% follow-up and participation in telephone interviews after enrollment for the Active Follow-up Sub-cohort. Thus, completed follow-up interviews are expected for approximately 13,500 workers and 4,500 controls in Years 3-4.

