Table 3 presents minimum detectable odds ratios across a range of proportions of exposure among the workers and of health outcome among the controls. Estimates are shown separately for analyses of the full cohort and of the Active Follow-up Sub-cohort, including all controls or including only the non-local controls. Estimates are also shown for analyses of the Biomedical Surveillance Sub-cohort. All estimates are based on a two-sided test with $\alpha=5\%$ and power=80%. As the table shows, this study has excellent power to detect small risks, except when exposure or outcome is rare. For example, in an analysis of the full cohort, if 10% of the workers received a given exposure (e.g., high exposure to VOCs) and the incidence or prevalence of disease is 1%, this study would have sufficient power to detect an OR of at least 1.56 when using all 12,000 controls and 1.86 when using only the 2,500 non-local controls. In an analysis restricted to the Active Follow-up Sub-cohort, with proportion of exposure of 10% and disease incidence/prevalence of 10%, the minimum detectable OR would be only 1.30 when using the full control group (N=5,000) and 1.38 for the non-local control group (N=1,500). The Biomedical Surveillance Sub-cohort, with 4,500 workers and 500 controls, provides adequate statistical power to detect odds ratios of at least 1.59 when 25% of workers received a given exposure and the incidence or prevalence of disease is 10%. For perspective, estimated relative risks of lower respiratory tract symptoms observed among clean-up workers in previous oil spills ranged from 1.5 to 3.6 [Janjua, et al. 2006, Zock, et al. 2007, Meo, et al. 2009, Sim, et al. 2010]. Thus GuLF STUDY is sufficiently powered to observe such prevalence or relative risks for these outcomes.

Table 3. Minimum detectable odds ratios for a range of proportions of exposure among the workers and for all controls vs. non-local controls, based on a two-sided test with $\alpha=5\%$ and power=80%

Size of control group (i.e., all vs. non-local)	Proportion (N) of workers exposed to a given agent					
	5%	10%	25%	50%	75%	100%
Full cohort: 43,000 workers, 12,000 controls:						
	N=2,150	N=4,300	N=10,750	N=21,500	N=32,250	N=43,000
Proportion of controls with outcome=1%						
12,000 ^a	1.74	1.56	1.41	1.35	1.33	1.32
2,500 ^b	2.02	1.86	1.76	1.72	1.71	1.70

Proportion of controls with outcome=10%

12,000 ^a	1.23	1.17	1.13	1.11	1.10	1.10

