Finally, power calculations indicate that even if participation rates turn out to be as much as 20% lower than expected, the minimum detectable ORs or differences will increase by less than 10-15%.

7 Analysis Plan

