The potential long-term health effects of participation in this and other clean-up efforts are largely unknown. The few previous studies examining health consequences of oil spills have reported respiratory, neurological, hematologic, and psychological or mental health related outcomes (see “Background” section below). Workers involved in the DWH oil spill have not only been exposed to the constituents of the oil but also to dispersants and oil & dispersant mixtures as well as to extended uncertainty and unemployment due to the long-term nature of the spill and its impact on the region. Thus they offer a unique opportunity to further understand exposure-response relationships and mental health outcomes associated with oil spills in general and this event, specifically. In response to concerns about potential health impact of the Deepwater Horizon oil spill, a cohort of nearly 33,000 persons involved in some aspect of oil spill clean-up has been surveyed regarding clean-up experiences and current health. A subgroup of 11,200 participants from Gulf states have completed brief clinical examinations at home during which lung function and blood pressure were measured and biological samples (blood, urine, toenails, hair) and environmental samples (dust wipes) were collected. The **GuLF STUDY Biomedical Surveillance Clinical Examination (BSCE)** which will be carried out among a subset of GuLF STUDY participants is designed to more thoroughly investigate the following questions related to potential health effects of this environmental disaster.

1. Are worker exposures to constituents of oil, dispersants, and oil & dispersant mixtures associated with adverse effects on respiratory and neurological function?
2. Are worker exposures or experiences related to the DWH oil spill resulting in measurable and sustained psychological or mental health related outcomes?
3. Are there biomarkers of potentially adverse biologic effects associated with oil spill-related exposures?

The proposed BSCE extends the work of the GuLF STUDY among a subgroup of participants who completed home visits (Active Surveillance Follow-up Cohort) by undertaking more intensive clinical testing and mental health evaluations (hereafter

referred to as “clinical examinations”). These additional clinical examinations will allow for a much more in-depth understanding of pulmonary, neurological, and mental health outcomes that may be associated with the DWH oil spill exposures and experiences.

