After multiple rounds of call attempts, reminder mailings, incentive offers, and targeted use of on-the-ground locating, approximately 61% of eligible participants have completed the first GuLF STUDY follow-up interview. To further reduce potential barriers to participation and collect minimal follow-up data on health status from non-responders, an abbreviated form has been developed which participants can complete by mail, web or telephone.

2 **Purpose:**

The purpose of this pilot test is to measure:

- a. participation in the abbreviated follow-up among non-responders for the full follow-up telephone interview;
- b. differences in participation among participants contacted by four approaches (mail, email mail + email, and neither; all participants will be contacted by telephone);
- c. differences in participation by mode of administration (mail, web, telephone).

3 **Eligible Participants:**

New strategies to increase retention and follow-up participation will be tested among 2,000 participants who have not been reached for follow-up telephone interviews after exhausting prior attempts by mail and phone. We will test each strategy with samples of 500 participants per approach. Participants will be selected from among those with and without email addresses on file and those who are and are not eligible for clinical exams. Participants reported as deceased or incapacitated are excluded as are those who asked to withdraw permanently from study participation.

Follow-up Interview Non-responders	All	Email Address	No email Address
Total	10,671	5,998	4,673
Not Eligible for Clinical Exam	9,509	5,390	4,119
Eligible for Clinical Exam	1,162	608	554
LSU	356	177	179
USA	806	431	375

4 **Methods:**

2,000 non-responders will be selected for the pilot test and will be randomized into four groups. Strategies being tested are summarized in the table below.

		Email contact	
		Used	Not Used
Mailed form	Used	
Group 1 N=500*
 
 • Send e-mail with web link • Send paper form after 7 days • Call after 4 weeks 	
Group 2 N=500
 
 • Send paper form • Call after 4 weeks
	Not Used	
Group 3 N=500
 
 • Send e-mail with web link • Call after 7 days 	
Group 4 N=500
 
 • Send advance letter (without paper form) • Call after 7 days

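### The full-cohort and Active Follow-up power figures still rest on 55,000 and 20,000 people, although a later addendum in the same protocol reports about 33,000 enrolled and 11,200 home examinations

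*Protocol*

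**What the plan says.** The Protocol Summary gives a sample size of 55,000. Section 6.5.1 states that "the total size of the full cohort is anticipated to be approximately 55,000 persons (43,000 workers and 12,000 controls"), made up of "20,000 members of the Active Follow-up Sub-cohort (15,000 workers and 5,000 controls") and 35,000 people followed passively. For the Active sub-cohort it adds: "we anticipate 90% follow-up and participation in telephone interviews after enrollment", and from this expects 13,500 worker and 4,500 control interviews, 18,000 in all.

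Tables 3 and 4 in Section 6.5.2 give minimum detectable odds ratios and differences at 80% power, two-sided 5%, for these sizes. The text describes the power as excellent for small risks unless exposure or outcome is rare. On under-recruitment it says "even if participation rates turn out to be as much as 20% lower than expected, the minimum detectable ORs or differences will increase by less"; the limit it names is 10-15%.

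Addendum 3, Section 1.A, reports that "a cohort of nearly 33,000 persons involved in some aspect of oil spill clean-up has been surveyed", and then: "A subgroup of 11,200 participants from Gulf states have completed brief clinical examinations at home". Addendum 6, Section 1, says that "approximately 61% of eligible participants have completed the first GuLF STUDY follow-up interview".

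**The concern.** The Summary gives the accrual period as 3/2011 to 03/2013 and the design as a closed cohort. Addendum 3 plans clinic examinations from May 2014 and describes the survey and home examinations as done. Its counts are therefore the achieved sizes, not an interim tally. The clinical examination was re-powered at N = 4,000 in Addendum 3, but the Summary and Section 6.5 were left as they were. The document thus holds a current power statement for one component and an outdated one for the two larger analysis sets.

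What is at stake is how null findings are read. Judged against the Section 6.5.2 tables, a null result for a modest effect or a rare outcome would be credited with sensitivity that the study does not have.

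**Working it through.** **Inputs.** Planned sizes, exposure and outcome proportions, alpha and power: Sections 6.5.1 and 6.5.2. Achieved sizes: Addendum 3, Section 1.A. Follow-up target group: Section 2.13.1. Non-responder counts: Addendum 6, Section 3. Assumption: the planned mixes (43:12 and 3:1) held, and the 11,200 are taken as the achieved Active sub-cohort.

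**Formulas.** n1 = exposed workers (10% of workers), n0 = controls.
- Binary outcome: solve p1 − p0 = 1.96·√[p̄(1−p̄)(1/n1+1/n0)] + 0.8416·√[p1(1−p1)/n1 + p0(1−p0)/n0], with p̄ the weighted mean and OR = p1(1−p0)/[p0(1−p1)].
- Continuous outcome: 2.8016·√(1/n1+1/n0), in SD.

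**Reproducing the plan.** 4,300 exposed against 12,000 controls, 1% outcome: OR 1.555 and 0.0498 SD (stated 1.56 and 0.050). 1,500 against 5,000, 10% outcome: OR 1.295 and 0.0825 SD (stated 1.30 and 0.082). The method is the protocol's own. One cell in the continuous-outcome table does not reproduce (Biomedical, 5% exposed: stated 0.217, computed 0.225); it has no bearing here.

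**Achieved sizes.** 33,000/55,000 = 60%, so 25,800 workers and 7,200 controls. 11,200/20,000 = 56%, so 8,400 and 2,800.

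| Analysis | n1 / n0 | OR, plan → achieved | SD, plan → achieved | Power at stated OR |
|---|---|---|---|---|
| Full cohort, 1% outcome | 2,580 / 7,200 | 1.56 → 1.74 | 0.050 → 0.064 | 61% |
| Active, 10% outcome | 840 / 2,800 | 1.30 → 1.40 | 0.082 → 0.110 | 58% |

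For the first row, p1 = 0.01725 and p̄ = 0.01191, so the right-hand side is 1.96·0.002489 + 0.8416·0.002819 = 0.00725, which equals p1 − p0. Detectable differences in SD rise by 1/√0.60 − 1 = 29% and 1/√0.56 − 1 = 34%. In the Active sub-cohort with a 1% outcome, the detectable OR goes from 1.98 to 2.38.

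**Sensitivity to the mix.** With controls at 10% to 30% of the total, the full-cohort OR is 1.73 to 1.85 (power at 1.56: 50% to 61%) and the Active OR is 1.40 to 1.46 (power at 1.30: 48% to 58%).

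**The 20% statement.** A 20% cut gives 1/√0.80 − 1 = 12%, so the statement is right for the shortfall it names. It does not reach 40% or 44%.

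**Follow-up of the Active sub-cohort.** 18,000 interviews cannot come from 11,200 people. At the planned 90%, 0.90 × 11,200 = 10,080 (7,560 workers, 2,520 controls). With 756 exposed against 2,520 controls and a 10% outcome, the OR is 1.43, against 1.31 for 13,500 and 4,500. The difference is 0.116 SD against 0.087.

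**The case against.** **The figures are labelled as anticipated and the arithmetic is right.** Both are true. The fault is that the section was not updated, not that it was miscalculated. A dated update beside the plan is enough, and the design rationale can stay.

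**The odds ratios themselves rise only 12% and 8%, which looks like the promised 10-15%.** In these two examples that is so. But an OR near 1 hides the change: its distance from 1 grows by 33% and 37%, and differences in SD grow by 29% and 34%.

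**The substantive conclusions survive.** Largely so for common outcomes. At OR 1.5 with 10% exposed and a 10% outcome, power is above 99% at 33,000 and 92% at 11,200, so the comparison with earlier respiratory relative risks of 1.5 to 3.6 holds there. Differences of 0.064 and 0.110 SD stay well below the 0.6 and 4.3 SD benchmarks in Section 6.5.2. The protocol also concedes limited power for rare outcomes. But its tables quantify that limit, and at OR 1.5 with a 1% outcome power is only 53% and 25%.

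**A reader might infer that follow-up fell from 90% to 61% and that power for follow-up outcomes collapsed.** The documents do not support this. The 90% is for the Active sub-cohort. Section 2.13.1 opened the first follow-up interview to all English- and Spanish-speaking participants, and the 61% refers to everyone eligible. Addendum 6 lists 10,671 non-responders, whereas 39% of 11,200 would be only 4,368. Instead 10,671/0.39 gives about 27,400 eligible and about 16,700 completed interviews across the cohort. The Active sub-cohort's own rate is not reported.

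**A reader might also extend the point to the Biomedical block.** Addendum 3 already re-plans it at about 4,000 examinations with about 23% non-workers. That gives 0.184, 0.137 and 0.105 SD at 10%, 25% and 100% exposed, against 0.182, 0.151 and 0.132 stated. It is worse only at 5% exposed (0.244 against 0.217).

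**Conclusion.** The concern stands for the full cohort and the Active Follow-up Sub-cohort. The Summary, Section 6.5.1 and two blocks of each power table state sizes that the same document shows were missed by 40% and 44%. At the achieved sizes, power at the stated odds ratios is about 61% and 58% instead of 80%, and the expected 18,000 Active follow-up interviews are impossible.

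The exact figures assume the planned worker-to-control mix. The direction does not: across 10% to 30% controls, power stays at or below about 61%. The loss falls on small effects and rare outcomes.

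**What to change.** - Add the achieved sizes, by worker status and dated, to the Protocol Summary and Section 6.5.1, beside the planned ones.
- Recompute the full-cohort and Active blocks of Tables 3 and 4, including the non-local control rows, and the worked examples in Section 6.5.2.
- Replace the 18,000 expected interviews. Report follow-up separately for the Active sub-cohort and the whole cohort, and do not apply the 61% to the Active group.
- Keep the robustness statement, but say that the achieved shortfall exceeds the 20% it covers.
- For the clinical examination, refer to Tables 6 and 7 of Addendum 3.

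The cost is recalculation and text, with no new participants or data. The downside is that the stated detectable effects become less favourable.

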6.5.2 Sample Power

This study is designed not around a few narrow *a priori* hypotheses, but rather to allow the investigation of a wide range of potential adverse health effects. The study size and the number of individuals who experienced a given exposure – and the consequent statistical power – have largely been determined by the number of individuals involved in the clean-up operations and their distribution by task/exposure. While this study will have limited power to examine certain rarer exposures or outcomes in the near future, this is the largest study to date of oil spill clean-up workers and it is important that we address, to the extent feasible, the wide range of public health concerns. It is a prospective study and as time passes, if the exposure continues to exert an impact on some health outcomes, power will increase.

Table 3 presents minimum detectable odds ratios across a range of proportions of exposure among the workers and of health outcome among the controls. Estimates are shown separately for analyses of the full cohort and of the Active Follow-up Sub-cohort, including all controls or including only the non-local controls. Estimates are also shown for analyses of the Biomedical Surveillance Sub-cohort. All estimates are based on a two-sided test with $\alpha=5\%$ and power=80%. As the table shows, this study has excellent power to detect small risks, except when exposure or outcome is rare. For example, in an analysis of the full cohort, if 10% of the workers received a given exposure (e.g., high exposure to VOCs) and the incidence or prevalence of disease is 1%, this study would have sufficient power to detect an OR of at least 1.56 when using all 12,000 controls and 1.86 when using only the 2,500 non-local controls. In an analysis restricted to the Active Follow-up Sub-cohort, with proportion of exposure of 10% and disease incidence/prevalence of 10%, the minimum detectable OR would be only 1.30 when using the full control group (N=5,000) and 1.38 for the non-local control group (N=1,500). The Biomedical Surveillance Sub-cohort, with 4,500 workers and 500 controls, provides adequate statistical power to detect odds ratios of at least 1.59 when 25% of workers received a given exposure and the incidence or prevalence of disease is 10%. For perspective, estimated relative risks of lower respiratory tract symptoms observed among clean-up workers in previous oil spills ranged from 1.5 to 3.6 [Janjua, et al. 2006, Zock, et al. 2007, Meo, et al. 2009, Sim, et al. 2010]. Thus GuLF STUDY is sufficiently powered to observe such prevalence or relative risks for these outcomes.

Table 3. Minimum detectable odds ratios for a range of proportions of exposure among the workers and for all controls vs. non-local controls, based on a two-sided test with $\alpha=5\%$ and power=80%

Size of control group (i.e., all vs. non-local)	Proportion (N) of workers exposed to a given agent					
	5%	10%	25%	50%	75%	100%
Full cohort: 43,000 workers, 12,000 controls:						
	N=2,150	N=4,300	N=10,750	N=21,500	N=32,250	N=43,000
Proportion of controls with outcome=1%						
12,000 ^a	1.74	1.56	1.41	1.35	1.33	1.32
2,500 ^b	2.02	1.86	1.76	1.72	1.71	1.70

Proportion of controls with outcome=10%

12,000 ^a	1.23	1.17	1.13	1.11	1.10	1.10
2,500 ^b	1.30	1.25	1.22	1.21	1.21	1.21

Proportion of controls with outcome=30%

12,000 ^a	1.15	1.11	1.08	1.07	1.07	1.07
2,500 ^b	1.19	1.16	1.14	1.14	1.14	1.13

Active Follow-up Sub-cohort: 15,000 workers, 5,000 controls:

	N=750	N=1,500	N=3,750	N=7,500	N=11,250	N=15,000
--	--------------	----------------	----------------	----------------	-----------------	-----------------

Proportion of controls with outcome=1%

5,000 ^a	2.33	1.98	1.71	1.59	1.55	1.53
1,500 ^b	2.66	2.34	2.11	2.02	1.99	1.97

Proportion of controls with outcome=10%

5,000 ^a	1.40	1.30	1.21	1.18	1.17	1.16
1,500 ^b	1.47	1.38	1.31	1.29	1.28	1.28

Proportion of controls with outcome=30%

5,000 ^a	1.26	1.19	1.14	1.12	1.11	1.11
1,500 ^b	1.31	1.25	1.20	1.19	1.18	1.18

Biomedical Surveillance Sub-cohort: 4,500 workers, 500 controls:

	N=225	N=450	N=1,125	N=2,250	N=3,375	N=4,500
--	--------------	--------------	----------------	----------------	----------------	----------------

Proportion of controls with outcome=1%

500 ^a	4.62	3.86	3.32	3.11	3.04	3.00
------------------	------	------	------	------	------	------

Proportion of controls with outcome=10%

500 ^a	1.92	1.73	1.59	1.54	1.53	1.52
------------------	------	------	------	------	------	------

Proportion of controls with outcome=30%

500 ^a	1.60	1.47	1.38	1.35	1.33	1.33
------------------	------	------	------	------	------	------

^a All controls in cohort/sub-cohort

^b Non-local controls in cohort/sub-cohort

Minimum detectable differences for continuous outcomes are presented in Table 4. Differences are expressed in standard deviations (SDs) and are based on a two-sided test with $\alpha=5\%$ and power=80%. Results are shown separately for analyses of the full cohort and of the Active Follow-up Sub-cohort including all controls or including only the non-local controls. In addition, estimates are shown for analyses of the Biomedical Surveillance Sub-cohort. This table demonstrates that the present study has sufficient

power to detect small differences in continuous outcomes. For example, in an analysis of the full cohort that examines an exposure of 10% prevalence, we will be able to detect minimum differences of less than 0.050 SD for the full cohort and 0.070 SD for the non-local cohort. A similar analysis in the Active Follow-up Sub-cohort will be able to detect minimum differences of less than 0.082 SD when using all 5,000 controls and 0.102 when using the 1,500 non-local controls. Such an analysis in the Biomedical Surveillance Sub-cohort will have sufficient power to detect a minimum difference of 0.182 SD. For perspective, in a study of volunteers involved in the Prestige oil spill clean-up and unexposed controls [Laffon, et al. 2006], results of the comet assay in peripheral blood leukocytes showed differences between the two groups of approximately 4.3 SD in comet tail length. A study of health effects related to the Tasman Spirit oil spill found a difference of about 0.6 SD in symptom scores between coastal residents affected by the spill and persons living away from the site of the spill [Janjua, et al. 2006]. The present study is very well powered to detect such effects.

Table 4. Minimum detectable differences, in standard deviations, for continuous outcomes for a range of proportions of exposure among the workers and for all controls vs. non-local controls, based on a two-sided test with $\alpha=5\%$ and power=80%

Size of control group (full vs. non-local)	Proportion of workers exposed to a given agent					
	5%	10%	25%	50%	75%	100%
Full cohort: 43,000 workers, 12,000 controls:						
	N=2,150	N=4,300	N=10,750	N=21,500	N=32,250	N=43,000
12,000 ^a	0.066	0.050	0.037	0.032	0.030	0.029
2,500 ^b	0.082	0.070	0.062	0.059	0.058	0.058
Active Follow-up Sub-cohort: 15,000 workers, 5,000 controls:						
	N=750	N=1,500	N=3,750	N=7,500	N=11,250	N=15,000
5,000 ^a	0.110	0.082	0.061	0.051	0.048	0.046
1,500 ^b	0.125	0.102	0.086	0.079	0.077	0.076
Biomedical Surveillance Sub-cohort: 4,500 workers, 500 controls:						
	N=225	N=450	N=1,125	N=2,250	N=3,375	N=4,500
500 ^a	0.217	0.182	0.151	0.139	0.134	0.132

^a All controls in cohort/sub-cohort

^b Non-local controls in cohort/sub-cohort

Finally, power calculations indicate that even if participation rates turn out to be as much as 20% lower than expected, the minimum detectable ORs or differences will increase by less than 10-15%.

7 Analysis Plan

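### Protocol section 6.5.2, Table 4: the detectable difference of 0.217 SD for the Biomedical Surveillance Sub-cohort at 5% exposure does not follow from the printed 225 exposed and 500 controls; it should be 0.225 SD

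*Protocol*

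**What the plan says.** Section 6.5.2 introduces Table 4 for continuous outcomes: "Differences are expressed in standard deviations (SDs) and are based on a two-sided test with $\alpha=5\%$ and power=80" per cent. The table's title repeats these settings: "all controls vs. non-local controls, based on a two-sided test with $\alpha=5\%$ and power=80" per cent.

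The last block of the table is headed "Biomedical Surveillance Sub-cohort: 4,500 workers, 500 controls". Its columns run over the proportion of workers exposed to a given agent: 5%, 10%, 25%, 50%, 75% and 100%. The exposed numbers printed beneath are 225, 450, 1,125, 2,250, 3,375 and 4,500, which are those percentages of 4,500. There is a single row, with 500 controls, footnoted as "All controls in cohort/sub-cohort". Its entries are "0.217 0.182 0.151 0.139 0.134 0.132".

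The 5% column therefore states that 225 exposed workers against 500 controls can detect 0.217 SD with 80% power.

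**The concern.** Every input to the cell is printed in the table or in the text that introduces it, so the cell can be checked directly. The first entry of the row does not agree with the group sizes above it, while the other five do. The error makes the figure look better than the design delivers, and it falls in the rarest-exposure column, where power is lowest. A reader planning an analysis of a rare agent in this sub-cohort would take 0.217 SD as detectable at 80% power when the printed numbers do not support that.

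**Working it through.** **Inputs, all from section 6.5.2.** Two-sided alpha 5%; power 80%; differences in SD units, so SD = 1; 500 controls; exposed numbers as printed in Table 4.

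**Formula.** For a two-sample comparison of means under the normal approximation, the minimum detectable difference is

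MDD = (z₀.₉₇₅ + z₀.₈₀) × √(1/n_exposed + 1/n_controls), with 1.960 + 0.8416 = 2.8016.

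**Step 1: reproduce the rest of the row, with 500 controls.**

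| Exposed | Printed | Computed |
|---|---|---|
| 450 | 0.182 | 0.1820 |
| 1,125 | 0.151 | 0.1506 |
| 2,250 | 0.139 | 0.1385 |
| 3,375 | 0.134 | 0.1343 |
| 4,500 | 0.132 | 0.1321 |

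All five agree to within rounding. So do the 24 cells of the other two blocks: across all 29 cells the deviation is at most about 0.0005 SD, and power at the printed difference lies between 79.5% and 80.6%. The formula is therefore consistent with the rest of the table.

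**Step 2: the 5% cell.**

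√(1/225 + 1/500) = √(0.004444 + 0.002) = 0.08028

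MDD = 2.8016 × 0.08028 = 0.2249, against 0.217 printed. The gap is 0.2249 − 0.217 = 0.0079 SD, and 0.0079/0.217 = 3.6%.

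**Step 3: power at the printed value.**

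Φ(0.217/0.08028 − 1.960) = Φ(0.743) = 0.771. That is 77.1%, or 2.9 points below the stated 80%.

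**Step 4: could another method give 0.217?**

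- A noncentral t calculation with 225 and 500 gives 0.225 SD, and 77.0% power at 0.217.
- A one-sided 5% test gives 0.200 SD.
- Keeping 225 exposed and solving for the controls gives about 643, a number that appears nowhere in the protocol.
- Keeping 500 controls and solving for the exposed gives about 250. Over the rounding range 0.2165 to 0.2175 this is 248 to 252, which excludes 225. Directly, 2.8016 × √(1/250 + 1/500) = 0.2170.

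**Step 5: is 225 or 250 the intended entry?** The odds-ratio table in the same section (its Table 3) uses the same sub-cohort and column and prints 4.62, 1.92 and 1.60 for control outcome proportions of 1%, 10% and 30%. With 225 exposed these compute as 4.621, 1.922 and 1.599. With 250 they would be 4.478, 1.885 and 1.575. So 225 is the consistent entry, and it is 5% of the 4,500 workers, as the column heading requires.

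**The case against.** The arithmetic is hard to dispute, so the case on the other side is about cause and consequence. Most of it stands.

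**Cause.** A reader might infer that the cell was computed with 250 exposed workers, 5% of the whole sub-cohort of 5,000. The fit is close, but the protocol shows no calculation and prints no 250 in the table. The neighbouring cells were plainly based on 4,500: the 10% cell fits 450, whereas 500 exposed would give 0.177. The 250 is a plausible explanation, not a documented fact.

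**Consequence.** A reader might also infer that the sub-cohort is underpowered for its blood-count, neurological and lung outcomes. The documents do not support that.

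- Section 6.5.2 says that study size and power were largely fixed by how many people took part in the clean-up and in which tasks. No sample size was set from this cell, and 0.217 SD is not a target effect anywhere.
- The text cites only the 10% cell of this row, 0.182 SD, which is correct. The effects it offers for perspective are about 0.6 SD and 4.3 SD, so its claim of good power for them holds equally at 0.225 SD.
- The same section accepts increases in detectable differences of up to 10–15% if participation falls short by 20%. A 3.6% change in one cell is small on that scale.
- Section 7.1 leaves the analysis of the clinical-protocol outcomes, including respiratory and neurologic effects, to a later protocol. Addendum 3 then re-plans the clinical examination at about 4,000 completed examinations and gives its own power tables. Its 5% entry of 0.203 SD reproduces for 200 against 3,800.
- Baseline blood counts are planned for all 6,250 persons tagged for the sub-cohort (sections 2.1.2 and 2.9.5), more than the 5,000 in this block.

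None of this makes 0.217 right. The row is still in the main protocol, and Addendum 3 does not correct it.

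**Conclusion.** The point holds as a minor, one-cell numerical error. With 225 exposed workers and 500 controls at two-sided 5% and 80% power, the minimum detectable difference is 0.225 SD, not 0.217 SD; power at 0.217 SD is about 77%. The 77% is the same 0.008 SD discrepancy seen from the other side, not a second defect.

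The conclusion rests on the table's own inputs and on a standard two-sample comparison of means, which reproduces all the other cells. The choice between the normal and the t calculation does not alter it. It does not depend on the 250 explanation. It does not extend to any other cell, to the odds-ratio table, to the conclusions in the text or to the power of the examination planned in Addendum 3.

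**What to change.** In Table 4 of Protocol section 6.5.2, Biomedical Surveillance block, 5% column, replace 0.217 with 0.225. Leave the printed 225 and the other five entries as they are. The sponsor may wish to check its own calculation to confirm where 0.217 came from, but the correction does not depend on that.

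The cost is one number. The stated figure becomes slightly less favourable; design, sample size, analysis, wording of the section and the Addendum 3 tables all stay unchanged.
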